6. INVESTIGATIONAL PRODUCT

6.1 Name and description of investigational product(s)

a) Rocuronium 10 mg/ml solution for infusion

Rocuronium bromide is indicated as an adjunct to general anaesthesia to facilitate tracheal intubation during routine sequence induction and to provide skeletal muscle relaxation during surgery.

b) Sugammadex (Bridion®) 100 mg/mL solution for injection

Bridion reverses neuromuscular blockade induced by rocuronium or vecuronium in adults, by selective binding with the relaxant agent.

6.2 Summary of findings from non-clinical studies

a) Rocuronium:

Preclinical data reveal no special hazard for humans based on conventional studies of safety pharmacology, repeated dose toxicity, genotoxicity, toxicity to reproduction and development. Carcinogenicity studies have not been performed with rocuronium bromide (11).

b) Sugammadex:

Preclinical data reveal no special hazard for humans based on conventional studies of safety pharmacology, repeated dose toxicity, genotoxicity potential, and toxicity to reproduction, local tolerance or compatibility with blood.

Sugammadex is rapidly cleared in preclinical species, although residual sugammadex was observed in bone and teeth of juvenile rats. Preclinical studies in young adult and mature rats demonstrate that sugammadex does not adversely affect tooth colour or bone quality, bone structure, or bone metabolism. Sugammadex has no effects on fracture repair and remodelling of bone (12).

6.3 Summary of findings from clinical studies

a) Rocuronium:

The standard intubation dose for geriatric patients and patients with hepatic and/or biliary tract disease and/or renal failure during routine anaesthesia is 0.6 mg/kg rocuronium bromide. Regardless of the anaesthetic technique used, the recommended infusion rate is 0.3-0.4 mg/kg/h. For children and adolescents the recommended intubation dose during routine anaesthesia and maintenance dose are similar to those

in adults. When used in overweight or obese patients (defined as patients with a body weight of 30% or more above ideal body weight) doses should be reduced taking into account ideal body weight. The following conditions may influence the pharmacokinetics and/or pharmacodynamics of Rocuronium: hepatic and/or biliary tract disease and renal failure, prolonged circulation time, neuromuscular disease, hypothermia, obesity, burns, hypokalaemia, hypermagnesaemia, hypocalcaemia, hypoproteinaemia, dehydration, acidosis, hypercapnia and cachexia (11).

b) Sugammadex:

The use of sugammadex in patients with severe renal impairment (including patients requiring dialysis ($\text{CrCl} < 30 \text{ mL/min}$)) is not recommended (see section 4.4).

Studies in patients with severe renal impairment do not provide sufficient safety information to support the use of sugammadex in these patients (see also section 5.1).

For mild and moderate renal impairment (creatinine clearance ≥ 30 and $< 80 \text{ mL/min}$): the dose recommendations are the same as for adults without renal impairment.

Even though the recovery times in elderly tend to be slower, the same dose recommendation as for adults should be followed.

In obese patients, the dose of sugammadex should be based on actual body weight. The same dose recommendations as for adults should be followed. For mild to moderate hepatic impairment are no dose adjustments required, as sugammadex is mainly excreted renally (12).

6.4 Summary of known and potential risks and benefits.

a) Rocuronium:

The most commonly occurring adverse drug reactions include injection site pain/reaction, changes in vital signs and prolonged neuromuscular block. The most frequently reported serious adverse drug reactions during post-marketing surveillance is 'anaphylactic and anaphylactoid reactions' and associated symptoms (11).

b) Sugammadex:

Sugammadex is administered concomitantly with neuromuscular blocking agents and anaesthetics in surgical patients. The causality of adverse events is therefore difficult to assess. The most commonly reported adverse reactions in surgical patients were cough, airway complication of anaesthesia, anaesthetic complications, procedural hypotension and procedural complication (Common ($\geq 1/100$ to $< 1/10$)).

The following adverse reactions were reported in placebo controlled trials where subjects received anaesthesia and/or neuromuscular blocking agents (1,078 subject exposures to sugammadex versus 544 to placebo) (12):

[Very common ($\geq 1/10$), common ($\geq 1/100$ to $< 1/10$), uncommon ($\geq 1/1,000$ to $< 1/100$), rare ($\geq 1/10,000$ to $< 1/1,000$), very rare ($< 1/10,000$)]

System organ class	Frequencies	Adverse reactions (Preferred terms)
Immune system disorders	Uncommon	Drug hypersensitivity reactions (see section 4.4)
Respiratory, thoracic and mediastinal disorders	Common	Cough
Injury, poisoning and procedural complications	Common	Airway complication of anaesthesia Anaesthetic complication (see section 4.4) Procedural hypotension Procedural complication

6.5 Description and justification of route of administration and dosage

a) Rocuronium:

Rocuronium bromide is administered intravenously (i.v.) either as a bolus injection or as a continuous infusion.

The standard intubating dose during routine anaesthesia is 0.6 mg rocuronium bromide per kg body weight, which results in adequate intubation conditions within 60 seconds in nearly all patients.

If rocuronium bromide is administered by continuous infusion, it is recommended to give a loading dose of 0.6 mg rocuronium bromide per kg body weight and, when the neuromuscular block starts to recover, to start administration by infusion. In adults under intravenous anaesthesia, the infusion rate required to maintain the neuromuscular block ranges from 0.3 - 0.6 mg/kg/h. Under inhalational anaesthesia the infusion rate ranges from 0.3 - 0.4 mg/kg/h (11).

b) Sugammadex:

Sugammadex should be administered intravenously as a single bolus injection.

A dose of 4 mg/kg sugammadex is recommended if recovery has reached at least 1-2 post-tetanic counts (PTC) following rocuronium or vecuronium induced blockade.

A dose of 2 mg/kg sugammadex is recommended, if spontaneous recovery has occurred up to at least the reappearance of T₂ following rocuronium or vecuronium induced blockade (12).

6.6 Dosages, dosage modifications and method of administration

a) Rocuronium:

In group A (deep NMB) and group B (moderate NMB), a bolus of 0.6 mg/kg rocuronium is administered intravenously before tracheal intubation. After tracheal intubation, intravenous infusion of rocuronium (0.3 to 0.4 mg/kg) is started in group A (deep NMB), when PTC is more than 0 and titrated towards PTC 0-1. In group B (moderate NMB), no additional rocuronium is administered after tracheal intubation.

b) Sugammadex:

The NMB is reversed with an intravenous bolus injection of 4 mg/kg in group A and 2 mg/kg in group B.

6.7 Preparation and labelling of Investigational Medicinal Product

Due to limited funding, use of known drugs with known effects and limited risks in this trial, we request a waiver for annex 13 labelling of the IMPs. The IMPs that will be used will be prepared, labelled and administered at the bedside as described in the summary of product characteristics and according to local protocols for routine patient care. The medication will be administered by the anaesthesiologist, who is not blinded. The syringes with the IMPs cannot be directly observed by the blinded researchers as they will be covered by use of the sterile drapes.

6.8 Drug accountability

The IMPs that will be used (Rocuronium and Sugammadex) are dispensed by the clinical trials unit of the pharmacy of the Radboudumc. The anaesthesiologists that prepare and administer the drug will perform drug accountability by logging the administered products and their corresponding batch numbers on patient level. We will store this information in the trial master file.

7. NON-INVESTIGATIONAL PRODUCT

Not applicable

8. METHODS

8.1 Study parameters/endpoints

8.1.1 Main study parameter/endpoint

Quality of recovery score (QOR-40 questionnaire) at 24 hours after extubation (appendix 1).

8.1.2 Secondary study parameters/endpoints

Questionnaires:

- Quality of recovery-40 score at 48 hrs after extubation, (appendix 1)

Medication use:

- Cumulative opiate use
- Cumulative use of other analgesics and anti-emetics

Intra-operative parameters:

- Surgical conditions; the Surgical Rating Scale (please see Table 2) is used to quantify the quality of the surgical field during the pneumoperitoneum phase (after introduction of the Hasson trocar, after introduction of all trocars and then every 15 minutes).
- Intra-operative complications (e.g. major bleeding, spleen or liver injury)
- Operation time, length of pneumoperitoneum, first warm ischemia time
- Estimated blood loss
- Conversion to open donor nephrectomy
- Conversion to hand-assisted donor nephrectomy

Clinical parameters:

- Components of pain scores (NRS 0-10):
 - Superficial wound pain score at 1, 6, 24, 48 hours (after extubation)
 - Deep intra-abdominal pain score at 1, 6, 24, 48 hours
 - Referred shoulder pain score at 1, 6, 24, 48 hours
- Post-operative nausea and/or vomiting (NRS)
- Time to reach discharge criteria*

* discharge criteria are: adequate pain control with oral medication, passage of flatus or defecation, intake of solid food tolerated, patient is mobilized and

independent and patient accepts discharge. Discharge criteria will be evaluated daily. If the donor for social reasons wants to stay longer (e.g. long distance from partner of child who are still hospitalized) the 'virtual' discharge date is listed. A physician who is independent and blinded (ward physician) is responsible for the actual discharge date.

Follow up after 4 weeks:

- 30 day complications
- Pain scores (NRS 0-10)
- Werk en zorg Questionnaire (appendix 2)

8.1.3 Other study parameters

Baseline parameters: age, gender, length, weight, body mass index, comorbidity, side of nephrectomy.

8.2 Randomisation, blinding and treatment allocation

Randomisation:

Computer-generated randomization (supported by our statistician) will be used with stratification for center. To ensure a balanced distribution, we will use block randomization.

Blinding and treatment allocation:

Blinding of the surgeons to the level of NMB is ensured by covering the hand with the neuromuscular monitoring equipment under the sterile drapes and the nerve stimulator and computer are placed behind the sterile drapes away from the surgeons. All study medications are prepared (and labeled 'study medicine') by the anesthesiologist or his/her assistant after opening the envelope containing the allocation of treatment. This will be done in the operating room before the surgeons enter. Surgeons, scrub nurses, postoperative care nurses and the investigator assessing the postoperative endpoints are blinded to group allocation. The attending anesthetic staff in the operating room is not blinded.

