4.4 Sample size calculation

A sample size of 48 patients per group is needed to provide 90% power to detect a 10-point difference in the quality of recovery score at 1 day after extubation (alpha 5%). A 10-point difference represents a minimal relevant difference (8). Based upon our previous study, the standard deviation is 15 points (9).

At the Radboudumc and LUMC, respectively 90 and 45 laparoscopic donor nephrectomies are performed annually. All eligible donors will be screened. With an inclusion rate of approximately 80%, we expect that the screening (and inclusion period) will be 11 months.

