10.1 Primary study parameter(s) and secondary study parameter(s)

For the primary analysis group A and B will be compared with regard to the primary end-point (QOR-40 score at day 1). Factorial ANOVA will be used to compare groups and to adjust for co-variates *i.e.* age, gender and side of nephrectomy. P-values < 0.05 will be considered statistically significant. All analyses will be performed on an intention-to-treat basis.

Study parameters/endpoints	Presentation of data (quantitative/qualitative)
Quality of recovery	Quantitative
Medication use	Quantitative
Pain	Quantitative
Surgical rating score	Quantitative
Nausea/vomiting	Quantitative
Surgical parameters	Quantitative
Evaluation of post-operative complications	Quantitative

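### Randomisation is stratified by centre but the primary model omits centre, so standard errors are too large and power is lost if the two centres differ.

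*Combined protocol and SAP*

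**What the plan says.** Section 8.2 states: "Computer-generated randomization (supported by our statistician) will be used with stratification for center". The next sentence adds blocks to keep the arms balanced. Section 3 names two centres, Radboudumc and LUMC.

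Section 10.1 gives the primary model: "Factorial ANOVA will be used to compare groups and to adjust for co-variates". The covariates that follow are "age, gender and side of nephrectomy". They are introduced by *i.e.*, so the list is closed. Neither centre nor a stratified analysis appears in section 10 or elsewhere in the document.

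The planning figures are in section 4.4: "A sample size of 48 patients per group is needed to provide 90% power to detect a 10-point difference", and "Based upon our previous study, the standard deviation is 15 points". The SD is referenced to the Leopard-2 trial, which the notes to Table 1 describe as single-centre.

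**The concern.** With stratified blocks, each arm has almost the same mix of patients from the two centres. A difference in mean QOR-40 between centres then largely cancels out of the treatment difference and does not add to its sampling error. An analysis that ignores centre does not use this. It counts the centre difference as unexplained variation between patients, and so overstates the standard error. If the centres differ, confidence intervals are too wide, the test is conservative, and the trial gives up the precision that stratification provided.

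A centre difference is plausible. The endpoint is patient-reported on the ward, and Appendix 1 includes items on support from doctors and nurses, sleep, food and feeling cold. The centres also have different surgical and anaesthetic leads. The planned SD comes from one centre, so the stated power makes no allowance for between-centre variation.

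**Working it through.** **Inputs from the documents.** Target difference 10, SD 15, power 90%, 48 per group (section 4.4). Significance threshold 0.05 (section 10.1). Allocation 1:1 (section 5.1). Annual volumes of 90 and 45 (section 4.4) give centre shares of 90/135 = 2/3 and 1/3, or 64 and 32 of 96 patients if recruitment follows volume.

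**Assumptions.** The centre difference D in mean QOR-40 is not given; a range of 0 to 20 points is used. The SD of 15 is read as within-centre because its source was a single-centre trial. The arms are taken as exactly balanced within centre.

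**Step 1: the plan's own figure.** n per group = 2 × (1.960 + 1.282)² × 15² / 10² = 47.3, rounded up to 48. This reproduces the plan with a two-sided 5% test (one-sided would give 39). Power at 48 per group is 90.4% by the normal approximation and 89.8% by the exact t test.

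**Step 2: formulas.**

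- True standard error: 15 × √(2/48) = 3.062, whatever the value of D.
- Residual SD without centre: √(225 + (2/3)(1/3)D²) = √(225 + (2/9)D²).
- Reported SE without centre: that SD × √(2/48).
- Power without centre: Φ((10 − 1.96 × reported SE) / 3.062).
- Actual type I error without centre: 2 × [1 − Φ(1.96 × reported SE / 3.062)].

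For D = 10, the residual SD is √247.2 = 15.72 and the reported SE is 3.210, which is 4.8% too large. Power is Φ((10 − 6.29)/3.062) = 88.7%.

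**Step 3: results without centre in the model.**

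| D (assumed) | Residual SD | Reported SE | Excess | Power | Type I error |
|---|---|---|---|---|---|
| 0 | 15.00 | 3.062 | 0% | 90.4% | 5.0% |
| 5 | 15.18 | 3.099 | 1.2% | 90.0% | 4.7% |
| 7.5 | 15.41 | 3.146 | 2.7% | 89.5% | 4.4% |
| 10 | 15.72 | 3.210 | 4.8% | 88.7% | 4.0% |
| 15 | 16.58 | 3.385 | 10.6% | 86.4% | 3.0% |
| 20 | 17.72 | 3.616 | 18.1% | 82.9% | 2.1% |

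With centre in the model, power is 90.4% and type I error 5.0% in every row.

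**Step 4: the loss in patients.** A correctly specified analysis reaches 88.7% power with about 45 per group and 86.4% with about 42. Omitting centre therefore wastes about 3 of 48 per group at D = 10 and about 6 at D = 15.

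**Step 5: simulation.** In 40,000 simulated trials per setting (64 and 32 patients, three covariates unrelated to outcome, t-based tests), the results without and with centre were:

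| D | Power without / with | Type I error without / with |
|---|---|---|
| 10 | 87.0% / 89.0% | 3.9% / 4.9% |
| 15 | 83.9% / 88.8% | 3.1% / 5.0% |
| 20 | 80.5% / 88.9% | 2.0% / 4.9% |

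At D = 0 power was 88.7% without centre and 88.8% with it, so adding the term costs nothing visible. Power is a little below the formula throughout because of the t distribution and chance imbalance in the covariates.

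**Step 6: sensitivity to the SD.** If 15 is instead the total SD across both centres, the within-centre SD at D = 10 is √(225 − 22.2) = 14.24. Power is then 91.6% without centre and 93.1% with it. At D = 20 the figures are 95.3% and 98.7%. The planned power is met either way, but the model without centre remains the less efficient one.

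**The case against.** The strongest counter-argument is that the loss depends on a number the documents do not contain, and that it is small over much of the assumed range. Up to 7.5 points the loss is under one percentage point of power. A visible loss needs a centre difference as large as the trial's minimal relevant difference of 10 points, or a full SD. Section 5.1 sets one intra-operative and one post-operative protocol for both sites, which should limit such differences, and the volumes of 90 and 45 bear on the patient split, not on mean QOR-40. Appendix 1 has 7 support and 12 well-being items; a 10-point gap from those alone needs about 10/19 ≈ 0.5 points on every item. The treatment estimate is not biased and type I error does not rise, so a significant result would stand.

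All of this is fair as to size, and it makes this a point about efficiency, not validity. It does not justify omitting centre: the text gives no reason for the omission, and including the term costs almost nothing if the centres turn out alike.

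A second objection also has force. Centre should not be added mechanically to every secondary analysis. Section 8.1.2 includes conversions and intra-operative complications, which may be rare, as well as repeated surgical ratings and time to reach discharge criteria. Section 10.1 names no separate models for these. This limits the remedy for secondary endpoints but leaves the change to the primary model untouched.

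**Conclusion.** The concern holds. The plan stratifies by centre and leaves centre out of a closed covariate list. If the centres differ, the reported standard error is too large and the test is conservative. The cost is about 2 percentage points of power for a 10-point centre difference and about 4 for 15 points; it is negligible at 5 points or fewer. These figures rest on an assumed centre difference, a 2:1 split, a within-centre SD of 15 and exact balance within centre. The flaw is modest and does not threaten validity, but the correction is cheap enough that it should be made.

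**What to change.** In section 10.1, add centre (Radboudumc, LUMC) to the covariates of the primary model as a main effect. State that no centre-by-treatment interaction is included, because a factorial ANOVA can otherwise be read as containing one. For secondary endpoints analysed with a comparable linear model, include centre in the same way. For rare events, repeated ratings and time to discharge criteria, name the method and say how centre is handled.

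For the primary model the cost is a few words and one degree of freedom. The sample size stays at 48 per group and no new data are needed. Fixing the term before unblinding also removes a later choice between models with and without the stratification factor.

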8.3 Study procedures

The peri-operative flowchart is shown in figure 1.

With regard to the primary hypothesis the QOR-40 score at pod 1 is the primary variable.

With regard to the secondary hypotheses variables and time-points of interest are shown in Table 3 and Table 4.

8.4 Withdrawal of individual subjects

Subjects can leave the study at any time for any reason if they wish to do so without any consequences. The investigator can decide to withdraw a subject from the study for urgent medical reasons.

8.5 Replacement of individual subjects after withdrawal

Patients withdrawing will be replaced, with a maximum of 10 patients.

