4.3 Exclusion criteria

A potential subject who meets any of the following criteria will be excluded from participation in this study:

- insufficient control of the Dutch language to read the patient information and to fill out the questionnaires
- chronic use of analgesics or psychotropic drugs
- use of NSAIDs shorter than 5 days before surgery
- known or suspect allergy to rocuronium or sugammadex
- neuromuscular disease
- indication for rapid sequence induction
- deficiency of vitamin K-dependent clotting factors, coagulopathy or use of coumarin derivatives.
- Peri-operative use of fusidic acid or flucloxacillin
- Severe renal impairment (creatinine clearance <30ml/min)
- Morbid obesity (BMI >35 kg/m²)

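### Sections 8.5 and 8.6 let up to 10 withdrawn donors, allocated or not, be replaced and not followed, which is not reconciled with the intention-to-treat analysis in 10.1

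*Combined protocol and SAP*

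**What the plan says.** All references are to the combined protocol and SAP.

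- **Who can withdraw (8.4).** Donors may stop whenever they choose, whatever the motive. In addition, "The investigator can decide to withdraw a subject from the study for urgent medical reasons". No time window is given.
- **What happens next (8.5, 8.6).** "Patients withdrawing will be replaced, with a maximum of 10 patients". Section 8.6, whose heading concerns withdrawal from treatment, says that there is no follow-up after withdrawal.
- **When allocation becomes known (8.2, 11.2).** Consent is taken on the day of admission, one day before surgery. The study drugs are prepared in the operating room "after opening the envelope containing the allocation of treatment".
- **Primary endpoint (8.1.1).** QOR-40 at 24 hours after extubation.
- **Analysis (10.1).** "All analyses will be performed on an intention-to-treat basis".
- **Size (4.4).** "A sample size of 48 patients per group is needed to provide 90% power to detect a 10-point difference", with a standard deviation of 15 and no allowance for dropout.

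The protocol does not define the intention-to-treat set, give a method for missing scores, or say which arm a replacement joins. It also does not say that a withdrawn donor's data are deleted or that the donor leaves the analysis set.

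**The concern.** Withdrawals fall into three periods, and sections 8.5 and 8.6 treat them alike.

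1. **After consent, before the envelope is opened.** The donor has no known allocation. Replacement is harmless.
2. **After the envelope is opened, before the 24-hour QOR-40.** The donor is allocated but has no primary outcome. Section 8.6 means that none will be sought, and section 8.5 brings in someone else.
3. **After the 24-hour QOR-40, for example before the four-week follow-up.** The primary outcome exists, and the donor must stay in the primary analysis.

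The second period is the problem. With no rule for missing scores, the primary comparison rests on donors who were observed plus substitutes, although it is labelled intention-to-treat. The rationale expects the depth of block to affect surgical conditions, so medical withdrawals could differ between arms in number or prognosis. If they do, the arm that loses more poor recoveries looks better than it should. Because replacement brings the total back to the planned number, a reader of the results would have little reason to suspect it.

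**Working it through.** **1. The plan's own figure.** Inputs from 4.4: difference 10, SD 15, power 90%, alpha 5%. Alpha is taken as two-sided, since a one-sided test would need only 39 per group.

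n per group = 2 × (1.960 + 1.282)² × 15² / 10² = 47.3, rounded up to 48.

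The stated 48 is reproduced, and power at 48 is 90.4% (89.8% with the t distribution). Replacement does not alter this figure.

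**2. How many donors could be affected.** Planned total 2 × 48 = 96; with the cap of 10, at most 106. The share replaced is at most 10/106 = 9.4%, or 10/58 = 17.2% of one arm if all fell there.

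**3. Size of the bias.** Assumptions, none of them in the documents: *a* and *b* allocated donors withdraw per arm without a 24-hour score; each would have scored *g* points below the observed donors of the same arm; replacements bring each arm back to 48 observed.

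Bias with replacement = g × [a/(48 + a) − b/(48 + b)]

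For the same withdrawals from 48 per arm with nobody replaced:

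Bias without replacement = g × (a − b)/48

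With g = 20:

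| Withdrawals | With replacement | Without replacement |
|---|---|---|
| 3 v 1 | 20 × (3/51 − 1/49) = 0.77 | 20 × 2/48 = 0.83 |
| 6 v 2 | 20 × (6/54 − 2/50) = 1.42 | 20 × 4/48 = 1.67 |
| 10 v 0 | 20 × 10/58 = 3.45 | 20 × 10/48 = 4.17 |

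The two columns are close, and the second is slightly larger. The figures therefore measure bias from missing outcomes, not harm done by replacement.

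**4. Range over the deficit, and the effect on the test.** Unadjusted standard error = 15 × √(2/48) = 3.06. Two-sided type I error = Φ(−1.96 + bias/3.06) + Φ(−1.96 − bias/3.06). Deficits of 7.5, 15 and 30 points are 0.5, 1 and 2 SD.

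| Split | Deficit 7.5 | Deficit 15 | Deficit 30 |
|---|---|---|---|
| 5 v 5, equal deficits | 0; 5.0% | 0; 5.0% | 0; 5.0% |
| 7 v 3 | 0.51; 5.3% | 1.03; 6.3% | 2.05; 10.3% |
| 10 v 0 | 1.29; 7.1% | 2.59; 13.5% | 5.17; 39.3% |

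(Each cell: bias in points; type I error.)

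**5. Power if replacement is restricted.** Ten even losses from 96 leave 43 per group and 87.1% power (86.3% with the t distribution). Randomising 48/(1 − 10/106) = 53 per group, 106 in all, leaves 48 per group and 90.4% after ten even losses, and gives 92.9% if nobody is lost.

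**The case against.** The strongest reply is that replacement alone does not break intention-to-treat. The bias arises because a randomised donor has no 24-hour score, which follows from 8.6 and the missing rule for absent scores. Banning replacement without changing 8.6 would leave the bias slightly larger, as step 3 shows. This stands, and it is why the repair must reach 8.6 and 10.1 as well as 8.5.

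A second reply is that the sizes rest on assumed deficits and splits. All ten withdrawals in one arm within about a day of surgery is extreme, and equal numbers with equal deficits give no bias. This also stands.

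A third reply is that some replaced donors will never have been allocated, because consent precedes the envelope by a day. That is true, but the text does not confine replacement to them. The heading of 8.6 speaks of withdrawal from treatment, and study drugs are prepared only once the envelope is open, so allocated donors are within its reach.

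Three stronger readings are tempting but not supported:

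- *Donors with a bad surgical course are swapped, arm for arm, until 48 per group is reached.* Section 8.5 gives only a cap of 10. It names neither a stopping number nor the arm a replacement joins.
- *Bleeding or reoperation leads to withdrawal.* Section 8.1.2 lists major bleeding and 30-day complications as outcomes to record. No section names such events as grounds for withdrawal.
- *A donor given an excluded antibiotic after allocation is removed and replaced.* The criterion "Peri-operative use of fusidic acid or flucloxacillin" in 4.3 governs entry of potential subjects. Nothing says that later use triggers withdrawal, so 4.3 needs no change on this account.

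**Conclusion.** The point holds as a failure to reconcile sections. Sections 8.5 and 8.6 permit allocated donors to be replaced and not followed, and 10.1 does not say how an intention-to-treat analysis then treats them. Replacement conceals the resulting loss of primary outcomes; it does not create the bias.

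At an assumed 20-point deficit the bias is about 0.8 points for 3 versus 1 withdrawals, or 0.77/3.06 = 0.25 of a standard error. It is 3.4 points, about a third of the 10-point target, in the extreme 10 versus 0 case. It is zero when numbers and deficits are equal in both arms. These figures further assume that every counted withdrawal falls between opening of the envelope and the 24-hour score, and that the test is not adjusted for covariates.

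The likely effect is modest, but the repair is cheap and concerns the primary comparison, so it should be made.

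**What to change.** (a) **Section 8.5.** Replace only donors who leave before their envelope is opened. Any extra donors recruited later take the next unused envelope of their centre.

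(b) **Section 10.1.** Define the intention-to-treat set as every donor whose envelope was opened, analysed in the allocated arm. Use any 24-hour score obtained, including from donors who withdraw afterwards. Report withdrawals by arm and reason.

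(c) **Section 8.6.** After withdrawal from treatment, still collect the 24-hour QOR-40 where the donor consents.

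(d) **Section 10.1.** Add a sensitivity analysis that sets missing 24-hour scores below the arm mean by a stated range, for example 7.5, 15 and 30 points, varied separately by arm.

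**Cost.** A few sentences and one further analysis. The number analysed may fall slightly below 48 per group: ten even losses from 96 leave about 87% power. Randomising up to 53 per group avoids this and stays within the 106 donors that 96 plus 10 replacements already implies. At the protocol's own rates, (90 + 45) × 0.80 = 108 donors a year, so 106 take about 11.8 months against 10.7 for 96. That is still inside the 12-month enrolment aim in section 3.
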